Ascorbic acid participates as a co-factor in multiple reactions, particularly acting as a potent antioxidant, in collagen, neuropeptide and carnitine synthesis, increasing iron absorption, inhibiting histamine release and stimulating the immune system. The main cause of increased requirements of vitamin C in type 2 diabetes mellitus is the high levels of oxidative stress caused by hyperglycemia.

Plasma vitamin C concentrations have been inversely correlated to glycosylated hemoglobin and fasting and postprandial blood glucose and oxidative stress, but not on lipid profiles. Diabetes has also been associated to periodontal disease and vitamin C supplementation together with dental maneuvers has been shown to improve chronic periodontitis in newly diagnosed type 2 diabetic subjects. Vitamin C has also been shown to reduce anxiety levels but not stress and depression scores in diabetes. Three-month supplementation of vitamins C and E decreased hypertension, blood glucose while increasing superoxide dismutase and glutathione levels.

Vitamin D

There is recent evidence in humans and animal models, suggesting that vitamin D may play an important role in the risk of developing type 2 diabetes mellitus. Vitamin D receptors are present in pancreatic β cells and in cells of the immune system. Additional to its well known role as the main regulator of calcium absorption, vitamin D intervenes in the beta endopeptidase calcium dependent cells. Some cohort studies in the United States and one in Finland have reported an association of vitamin D and risk of type 2 diabetes mellitus. Other studies have found an association between serum vitamin D, insulin resistance and cell β dysfunction.

On the other hand, it has been demonstrated that vitamin D constitutes a predictor of death by cardiovascular disease (CVD) in patients with type 2 diabetes mellitus.

Zinc

Zinc has been widely studied in relation to diabetes mellitus, as it acts as an insulin mimetic and has a role in the regulation of oxidative stress, thus its supplementation may benefit patients with type 2 diabetes mellitus.

It has been shown that zinc supplementation may reduce glucose and HbA1c concentrations in diabetic subjects, contributing to an adequate metabolic control of the disease. High levels of serum zinc have been associated to lower risk of CVD in diabetic patients. Zinc supplementation has been suggested as an additional treatment for metabolic control in type 2 diabetic patients as it promotes insulin signalling. Inflammatory cytokines in type 2 diabetes mellitus are associated to zinc metabolism by zinc transporter and metallothionein gene expression.

Gut microbiota

The adult intestinal microbiota is composed of hundreds to thousands of species, dominated by the Bacteroidetes and Firmicutes phyla. This ecosystem is different and unique, since it includes many species that do not exist in another part of nature, which indicates powerful selective mechanisms that have generated a coevolution of the host with its intestinal microbial symbionts (commensal and mutualists). The adult intestinal microbiota is also partially stable, composed of approximately 40 bacterial species (representing 75% of the intestinal microbiota in terms of abundance).

In recent years, much attention has been given to the microbial community within the human body and its association to the immune system as well as to the development of chronic diseases such as obesity and type 2 diabetes mellitus. There are many factors involved in the health of this microbiota, such as genetics, environment, use of medications and particularly diet. Some types of microorganisms in the microbiota may promote inflammation increasing the risk for chronic diseases. Increased microbial diversity has been associated to decreased inflammation. Dysbiosis of gut microbiota has been associated to insulin resistance and glucose homeostasis as well as low-grade inflammation. It has been identified that the effect on insulin metabolism is through the regulation of insulin signalling molecules such as GLP-1 and PYY, which reduce insulin resistance and improvement of β -cell function.

There is not much information on the effect of zinc or vitamin C supplementation on gut microbiota. However, Vitamin D may promote a reduction in opportunistic pathogens and an increase in bacterial diversity in the gut. Vitamin D and its receptor (VDR) help in controlling dysbiosis, maintaining gut tolerance and protecting from chronic gastrointestinal diseases, through regulating microbiota composition and function in the intestine.

Oxidative stress

There is evidence that oxidative stress, defined as a persistent imbalance between the production of highly reactive molecular species (chiefly oxygen and nitrogen) and antioxidant defenses, leads to tissue damage. Oxidative stress results from increased content of reactive oxygen species (ROS) for example: superoxide and the hydroxyl radical, and uncharged species such as hydrogen peroxide. There are data indicating that ROS formation is a direct consequence of hyperglycemia; more recent studies have suggested that increased free fatty acid levels may also result in ROS formation. Because of their ability to directly oxidize and damage DNA, protein, and lipid, ROS are believed to play a key direct role in the pathogenesis of late diabetic complications.

Previous experimental and clinical studies report that oxidative stress plays a major role in the pathogenesis and development of complications of diabetes mellitus. However, the exact mechanism by which oxidative stress could contribute to and accelerate the development of complications in diabetic mellitus is only partly known and remains to be clarified. Hyperglycemia induces free radical production; on the other hand, it impairs the endogenous antioxidant defense system in patients with diabetes. Endogenous antioxidant defense mechanisms include both enzymatic and non-enzymatic pathways. Their functions in human cells are to counterbalance toxic reactive oxygen species (ROS). Common antioxidants include the vitamins A, C, and E, glutathione (GSH), and the enzymes superoxide dismutase (SOD), catalase (CAT), glutathione peroxidase (GPx), and glutathione reductase (GRx).

In diabetes, oxidative stress is caused by increased formation of plasma-free radicals and a reduction in antioxidant defenses. Hyperinsulinemia and hyperglycemia may enhance the production of free radicals and induce oxidative stress. There is considerable evidence that oxidative stress plays a key role in insulin resistance, impaired insulin secretion, and many of the complications of diabetes such as micro-/macro-vascular damage. SOD and GPx are antioxidant enzymes that protect the body against active oxygen-free radicals. Some experimental studies showed that Vitamin D may have antioxidant properties by modifying some of the antioxidant enzymes.

2. Problem

Chronic diseases have become one of the most important public health problems in the world, due to the high costs of treatment and control of complications. Changes in human behaviour and lifestyles in the last century have caused an increase in type 2 diabetes mellitus.

Chronic elevation of blood glucose, even in absence of symptoms, causes damage in several tissues, particularly microcirculation in the retina, kidneys and peripheral

nerves, where the diabetic complications are more evident. This has led to an increase in the incidence of blindness, amputations and renal failure in many countries, developed and developing. Individuals with diabetes have a two to four-fold higher risk than the general population of developing cardiovascular disease; between 50 and 80% of patients with diabetes die of heart disease or its complications, which also favour the development of disabilities, decrease in life expectancy and the use of a large amount of the health services' budget.

In Mexico, the situation of the health service system is complex, as there is a co-existence of chronic and infectious diseases. Type 2 Diabetes Mellitus was prevalent in 8 to 9% of the Mexican population and it is estimated to increase to 12.3% by the year 2025. Since 1940, diabetes has been in the list of the first 20 main causes of mortality, but since 2000, it is the first cause of death in women and the second in men (after ischemia). In 2003, diabetes caused 12.6% of all deaths in the Mexican population, with a mean age of death of 66 years. However, the National Nutrition Survey of 2012 (ENSANUT 2012) indicated that 9.2% of Mexican adults have been diagnosed with diabetes. It is also the main cause of medical outpatient attention and hospitalization.

Until now, researchers consider that the aetiology of type 2 diabetes mellitus is unknown. There are several hypotheses that try to explain the origin of the disease, such as that it is a disorder of the anterior hypothalamus and the endocrine pancreas caused by progressive ischemia or that there is an abnormal innervation of the islets. Recently, the study of the innate immune system has thrown some light, as there is increasing evidence of an inflammatory acute phase response induced by cytokines, closely linked with the generation of insulin resistance and diabetes. Other studies have associated these pathologies with the presence of inflammatory and immune biomarkers such as TNF- α , IL-1, IL-6, C Reactive Protein (PCR), Monocyte Chemotactic Protein-1 (MCP-1), sialic acid, leptin, adiponectin, resistin and visfatin.

Next to inflammation, patients with diabetes face greater risk of certain infections, including influenza, pneumonia, and foot infections. These infections are associated with increased morbidity and mortality.

Dysbiosis of gut microbiota has also been associated to insulin resistance and low-grade chronic inflammation in the development of type 2 diabetes mellitus.

There is evidence suggesting that supplementation with vitamin C, vitamin D or zinc may help patients with type 2 diabetes mellitus achieve a better metabolic control, thus aiding in the prevention of complications at various levels.

Hypothesis:

1. Vitamin C, vitamin D and zinc supplementation decreases pro inflammatory cytokines (TNF α , IFN- γ , IL-1 β) and improves anti-inflammatory (IL4, IL-6, IL10, TGF- β) in patients with type 2 diabetes mellitus.
2. Type 2 diabetes mellitus patients supplemented with vitamin C, vitamin D and zinc will have a better metabolic control.
3. Microbiota of patients with Type 2 diabetes mellitus will have a better profile after supplementation with vitamin C, vitamin D and zinc.
4. Vitamin C, vitamin D and zinc supplementation decreases oxidative stress levels (MDA and protein carbonyl) and improves antioxidant systems

(antioxidant capacity, enzymatic activity: catalase, superoxide dismutase and glutathione peroxidase) in patients with type 2 diabetes mellitus.

3. Objectives

General objective:

To evaluate the effect of vitamin C, vitamin D and zinc supplementation on glucose metabolism, inflammatory and immune system biomarkers, oxidative stress and gut microbiota in patients with type 2 diabetes mellitus in the State of Mexico.

Specific objectives:

1. To evaluate the effect of vitamin C, vitamin D and zinc supplementation on metabolic control (plasma glucose, HOMA, Hb1Ac and lipid profile).
2. To analyse the effect of vitamin C, vitamin D and zinc supplementation on inflammatory and immune biomarkers.
3. To analyse the effect of vitamin C, vitamin D and zinc supplementation on oxidative stress and antioxidant profile.
4. To evaluate the effect of vitamin C, vitamin D and zinc supplementation on gut microbiota.

4. Methods

Study design

Clinical trial randomized, prospective, placebo-controlled, double blinded, comparing two groups of patients with type 2 diabetes mellitus in the State of Mexico.

According to the calculation of the sample size, we will include 120 adults with type 2 diabetes mellitus selected from the outpatient preventive medicine offices of health centres in the State of Mexico who will be divided in two groups: supplement and placebo (60 per group). After having been invited to participate and obtaining the informed consent, study subjects will be evaluated for dietary information, as well as biochemical biomarkers of metabolic control, anthropometric, immune and inflammatory markers, gut microbiota and oxidative stress, before beginning the trial, and after 12 and 24 weeks of supplementation. They will have a monthly follow-up visit for evaluation of adherence and adverse effects, as well as delivery of the supplement.

Study groups

Subjects will be randomly allocated to a supplementation with 1000 mg vitamin C, 400 IU vitamin D and 10 mg of zinc or placebo group, during 24 weeks. Subjects and researchers will be blinded to the supplement or placebo in order to guarantee double-blinding.

Sample size calculations:

Based on a previous study done by this same research group (*Nutrients* 2017, 9, 573; doi:10.3390/nu9060573), we calculated the sample size with the data on the effect of a

6-month *n*-3 fatty acid supplementation trial on glucose concentrations of group of subjects with type 2 diabetes mellitus,

The calculations were done with the following formula:

$$N = \frac{(2 \times s^2)(Z\alpha + Z\beta)^2}{d^2}$$

Where: $Z_{\alpha/2} = 1.96$, $Z_{\beta} = 0.84$, $s = 68.9$ mg/dL and $d = 40$ mg/dL

Thus:

$$N = \frac{(2 \times 4747.21)(1.96 + 0.84)^2}{40^2} = 46 \approx 50 \text{ subjects}$$

Accounting for a 20% loss at follow-up, we added 10 subjects, resulting in 60 subjects per group. This sample size guarantees that we should be able to observe significant differences in all the other indicators we will measure.

The following criteria will be used for the selection of the study sample:

Inclusion criteria

- Between 25 and 55 years of age, as this is the age in which type 2 diabetes mellitus is more prevalent and there is less probability of encountering multiple diseases in the same subjects
- Both sexes
- Outpatients
- BIM ≥ 25

Exclusion criteria

- Without any other chronic disease (cancer, cardiovascular diseases, arthritis and Alzheimer's).
- Severe renal insufficiency.
- Nephrolithiasis or history of nephrolithiasis.
- Hyperoxaluria.
- Hemochromatosis.
- Hypercalcaemia.
- Hypervitaminosis D.
- Using insulin.
- Be taking drugs such as desferrioxamine, iron, cyclosporine, indinavir (protease inhibitors), warfarin, thiazide diuretic, orlistat, ion exchange resins (e.g. cholestyramine, laxatives (e.g. mineral oil, senna), vitamin d analogues (e.g. ergocalciferol, calcitriol, and topical calcipotriene), tetracycline antibiotics, quinolone antibiotics, penicillamine, biphosphonates, levothyroxine, eltrombopag).
- Patients with hypersensitivity to any of the active substance(s) or to any of the excipients.
- Hypersensitivity to the by-products including honey, conifers, poplars, Peru balsam, and salicylate.

- Intake of probiotics or supplemental vitamin or mineral (vitamin D, C, zinc or calcium) for 4 weeks before the beginning of the study.
- Smoking and alcohol consumption (> 40 gr/ day for men and 25 gr/ day for women).
- Pregnant or lactating.
- Whose parents or grandparents are/were immigrant or of native origin.

Measurements.

Subjects will be selected from the outpatient preventive medicine offices of health centres in the State of Mexico. After having been invited to participate and obtaining their informed consent, study subjects will be evaluated for dietary information, as well as biochemical, anthropometric, immune and inflammatory markers, as well as intestinal microbiota before beginning the trial, at 12 and 24 weeks of supplementation.

A qualified physician will do a complete clinical history. Subjects will be requested to fill-out the Diabetes 39 quality of life questionnaire (validated in Mexico), at baseline and at the end of the study. Questions on frequency of respiratory, urinary and gastrointestinal infections as well as on perception with respect to the supplement will be included.

A standardized nutritionist will evaluate Dietary History, a food-frequency questionnaire (FFQ), as well as three 24-hour food registry of non-consecutive days including one from the weekend. The FFQ will be analysed in DIAL software to evaluate dietary intake of vitamin C, vitamin D and zinc. Anthropometric evaluations will be done by a standardized nutritionist; weight will be measured with a 1631 TANITA™ portable electronic scale, stature with a 1013522 SECA™ portable stadiometer, for the calculation of BMI.

Faecal samples will be obtained for evaluation of intestinal microbiota. We will proceed to isolate and characterize the bacteria obtained from the faecal samples with two enriched culture media for the purification of the most representative and abundant strains. The isolated strains will be classified in morphological groups according to their macroscopic characteristics of size, form, surface, consistency and color. A selection of 40% of the representative samples from each morphologic group will be typified by the RFLP method. We will obtain biomass and extract DNA, for amplification of the 16S rRNA gene, with an enzymatic genotyping and strain grouping. The strains will be grouped to compare their diversity; the results of the groups will be compared to appreciate the differences between the type and number of strains obtained.

At each sampling date, a venous blood sample of 8.5 mL will be obtained after a 12 hour fast for the measurement of vitamin C (HPLC); zinc (Atomic Absorption Spectrometry); vitamin D and Vitamin D binding protein (ELISA); plasma glucose; triacylglycerides; total cholesterol; HDL and LDL-cholesterol and Hb1Ac (Automated Selectra equipment with Randox™ reactants); pro inflammatory cytokines (TNF α , IFN- γ , IL-1 β) and anti-inflammatory cytokines (IL4, IL-6, IL10, TGF- β), apolipoproteins A and B, C-reactive protein, V-CAM, I-CAM, complement proteins C-3 and C-4, insulin, adiponectin, resistin and leptin will be analysed with multiplex technology (Milliplex Luminex™). Additionally we will measure biomarkers of oxidative stress and

antioxidant systems such as Malondialdehyde (QuantiChrom™ TBARS Assay Kit), protein carbonyls (calorimetric assay), antioxidant capacity (QuantiChrom™ Antioxidant Assay Kit), Catalase activity (EnzyChrom™ Catalase Assay Kit), Superoxide Dismutase activity (EnzyChrom™ Superoxido Dismutase Assay Kit) and Glutathione Peroxidase (metaphosphoric acid SIGMA ALDRICH and EnzyChrom™ GSH/GSSG Assay Kit).

HOMA-IR and HOMA-B

HOMA_{IR} will be calculated as follows: HOMA_{IR} = (insulin x glucose)/405

HOMA-B will be calculated as follows: HOMA-B = 20 × insulin (μUI/mL) / (glucose [mmol/L] – 3,5) (160).

Follow-up

Additionally to their monthly visits to the clinic, the researchers will maintain close communication via telephone or e-mail with all participants, to promote adherence, and to identify any possible adverse effect of the supplements. Adherence will be evaluated by the Morisky-Green and Haynes-Sackett tests.

The investigators will collect, document, report and follow-up all events that meet the definition of an adverse event (AE) or serious adverse event (SAE) to the Health Authority (COFEPRIS) or the Ethics Committee in accordance with local legal obligations. AEs/SAEs will be collected from the first day the subject consumes the supplement up to three months after end of supplementation.

Adverse effects will also be registered during the monthly follow-up visits. If an adverse effect that puts the subject at risk is identified, such as an allergy, the supplementation will be suspended and reported to the authorities (COFEPRIS), as well as the producers of the supplement.

Bioethics

This project will be conducted according to the Declaration of Helsinki and all its amendments, including the one in 2013. We will also abide by the General Health Law of the Mexican Ministry of Health with respect to research in human beings.

The protocol will be reviewed and approved by the Research and Ethics Committees of the Faculty of Medicine of the Universidad Autónoma del Estado de México.

Participation in the study will be totally free and voluntary, subject to the participants' authorization by the signature of a letter of informed consent.

The procedures in the present study are considered with a risk higher than minimum, due to the need to draw blood by venipuncture.

All information will be maintained confidential.

Data Collection and Statistical Analysis

A specific database will be designed in SPSS 19.0®. Data will be described with means and standard deviations or frequencies and percentages depending on the type of data. We will undertake a normality analysis, after which differences between groups will be analysed by parametric or non-parametric statistical tests. A multiple regression analysis will be run in order to establish interactions between variables.

References

Barengolts E. Vitamin D and prebiotics may benefit the intestinal microbacteria and improve glucose homeostasis in prediabetes and type 2 diabetes. *Endocr Pract* 2013; **19**(3): 497-510. doi: 10.4158/EP12263.RA.

Crook M. Type 2 diabetes mellitus: a disease of the innate immune system? An update. *Diabetic Medicine*. 2003; **21**:203-7.

Diabetes Public Health. From Data to Policy: Oxford University Press; 2011

Encuesta Nacional de Salud y Nutrición 2012. http://www.insp.mx/ensanut/resultados_ensanut.html.

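### Glucose at week 24 can only be inferred as the primary outcome: the plan does not name it or fix a visit, and it has no multiplicity rule or criterion for calling a hypothesis supported

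*Combined protocol and SAP*

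**What the plan says.** **Hypotheses and objectives.** Section 2 ends with four unranked hypotheses, and section 3 lists four unranked specific objectives. Hypothesis 2 is general: "Type 2 diabetes mellitus patients supplemented with vitamin C, vitamin D and zinc will have a better metabolic control". Objective 1 spells it out: "To evaluate the effect of vitamin C, vitamin D and zinc supplementation on metabolic control (plasma glucose, HOMA, Hb1Ac and lipid profile". Hypothesis 1 names seven cytokines, with a direction for the pro-inflammatory and the anti-inflammatory group. Hypothesis 4 names six markers: "Vitamin C, vitamin D and zinc supplementation decreases oxidative stress levels (MDA and protein carbonyl) and improves antioxidant systems", the antioxidant part being antioxidant capacity and three enzymes.

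**Sizing.** Section 4, Sample size calculations, uses one variable, taken from an earlier 6-month "fatty acid supplementation trial on glucose concentrations of group of subjects with type 2 diabetes mellitus". It then says of everything else: "This sample size guarantees that we should be able to observe significant differences in all the other indicators we will measure".

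**Visits.** Under Study design and Measurements, assessments are at baseline and at weeks 12 and 24. No visit is named for the main comparison.

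**Analysis.** Data Collection and Statistical Analysis provides descriptive statistics and a normality check, after which "differences between groups will be analysed by parametric or non-parametric statistical tests". It adds: "A multiple regression analysis will be run in order to establish interactions between variables". For the microbiota, Measurements says only that "the results of the groups will be compared to appreciate the differences between the type and number of strains obtained". The section names no primary outcome, analysis visit, significance level, multiplicity method or rule for deciding that a hypothesis is supported.

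**The concern.** A single glucose test fixed in advance at one visit would keep its 5% error rate. The plan does not fix one. Glucose could be judged at week 12 or week 24, and by a test chosen after a normality check. Each of the other hypotheses covers several markers, and the plan does not say how many must differ. The sample-size text expects significant differences in the other indicators, so those markers are not presented as exploratory.

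Followed as written, the plan would let a hypothesis be called supported by whichever marker or visit fell below 0.05. A reader of the results could not check from the plan that the emphasised result was the one intended. That cannot be repaired credibly after unblinding.

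**Working it through.** **1. The plan's own figure.** Inputs from Sample size calculations: Z values 1.96 and 0.84, s = 68.9 mg/dL, d = 40 mg/dL.

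N = 2 × 4747.21 × (1.96 + 0.84)² / 40² = 46.52. The plan gives 46, rounds to 50, and adds 10 for losses to reach 60 per group. The value 1.96 implies a two-sided 5% level, which I apply to all tests because the analysis section gives none.

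**2. Glucose alone, either visit counted.** With no true effect, the chance is 1 − P(|Z₁₂| < 1.96 and |Z₂₄| < 1.96) for two correlated normal statistics. The documents give no between-visit correlation, so it is assumed:

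| Between-visit correlation | False-positive chance |
|---|---|
| 0.3 | 9.5% |
| 0.7 | 8.3% |
| 0.9 | 7.0% |

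**3. Marker counts.**
- Hypothesis 1: 7 cytokines.
- Hypothesis 4: 2 oxidative markers + 4 antioxidant markers = 6.
- Objective 1: glucose, HbA1c, HOMA-IR, HOMA-B and four lipids = 8. It would be 7 if HOMA means one index; the Methods define two.

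**4. Any one marker enough, one visit.** For independent tests the chance is 1 − 0.95^k if either direction counts. If only a favourable difference counts, it is 1 − 0.975^k. For example, 1 − 0.95⁶ = 0.265 and 1 − 0.975⁶ = 0.141. For correlated tests I integrated the equicorrelated normal model, with markers coded so that favourable is positive. The correlations are assumed.

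| Set | k | Either direction, r = 0.7 | Either direction, r = 0 | Favourable only, r = 0.7 | Favourable only, r = 0 |
|---|---|---|---|---|---|
| Hypothesis 4 | 6 | 16.4% | 26.5% | 8.2% | 14.1% |
| Hypothesis 1 | 7 | 17.8% | 30.2% | 8.9% | 16.2% |
| Objective 1 | 8 | 19.1% | 33.7% | 9.5% | 18.3% |

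The nominal rate for one test is 5% in the either-direction columns and 2.5% in the favourable-only columns. For objective 1 the r = 0 entries are upper limits: HOMA-IR and HOMA-B are computed from the same glucose and insulin, and glucose is itself in the set, so independence cannot hold. Nor is r = 0.7 a floor. At r = 0.9 the either-direction figures are 11% to 12%.

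**5. Power of a single glucose primary.** With 60 × 0.8 = 48 completers per group, 40 / (68.9 × √(2/48)) = 2.844 and Φ(2.844 − 1.96) = 0.81. Adjusting for baseline multiplies the standard error by √(1 − ρ²). Power is then 0.85 at ρ = 0.3 and 0.98 at ρ = 0.7, but only if s is the SD of week-24 values, which the documents do not say.

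**The case against.** **The primary outcome is evident.** Glucose is the only sizing variable, the sizing data come from a 6-month trial, supplementation lasts 24 weeks, and the rest are called other indicators. This stands as an inference, and it rules out saying that the plan points to no primary outcome. An inference does not fix the visit or the test, though, and hypotheses 1, 3 and 4 do not concern glucose.

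**The hypotheses are directional.** Hypotheses 1 and 4 state which way the markers should move, so an adverse difference would not support them. This stands, and it is why the favourable-only columns are shown. They are lower, but still more than three times the 2.5% nominal rate over the range shown. The analysis section does not itself restrict direction.

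**The any-one-marker rule is not in the plan.** This also stands. Hypotheses 1 and 4 join a decrease and an improvement, which can be read as requiring a pattern. If every marker had to differ, there would be no inflation. The percentages describe one scenario that the plan leaves open.

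**A stronger reading to avoid.** A reader might infer that hypotheses 1 and 4 and objective 1 each carry a 16% to 34% error rate. That range spans three different sets: hypothesis 4 does not exceed 26%, and 34% needs eight independent measures, which objective 1 cannot supply.

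**Conclusion.** The point holds as a gap with consequences for the error rate. The plan does not label its primary outcome, fix the visit, rank or adjust the other tests, or say what counts as support. The best-grounded figure is for glucose itself: about 7% to 9.5% instead of 5% if either visit may count. The larger figures for hypotheses 1 and 4 and objective 1 depend on three assumptions: 5% two-sided tests taken from the sizing formula, any one marker being enough, and correlations between 0 and 0.7. Higher correlations give less. The documents do not support treating these figures as the trial's known error rate, because they state neither a decision rule nor the correlations.

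**What to change.** Before unblinding, amend the objectives, the sample-size text and the analysis section as follows.

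- **Primary.** Name the between-group difference in fasting plasma glucose at week 24 as the single primary outcome at two-sided 5%. Analyse it by ANCOVA on group and baseline glucose, reported in mg/dL with a 95% CI. Any rank-based or transformed analysis is a sensitivity analysis.
- **Secondary.** List the other week-24 markers by objective. Objective 1 would hold the seven measures other than glucose, and objective 3 the six oxidative and antioxidant markers. For objective 2, say whether the family is the seven cytokines of hypothesis 1 or the wider inflammatory and immune panel. That panel has 15: the cytokines, C-reactive protein, V-CAM, I-CAM, C-3, C-4, adiponectin, resistin and leptin. For objective 4, name the microbiota variables. Either state one multiplicity method within each family (Benjamini-Hochberg at 5%, for example) or report these outcomes with 95% CIs as supportive only.
- **Exploratory.** Label week-12 results and the regression interactions as exploratory.

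**Cost.** This is text only, with no new data or participants. The primary keeps about 81% power with 48 per group, and more with ANCOVA under the condition given in step 5 of the working. If secondaries are adjusted, the worst case is one real effect in a family, tested at 0.05/m. The effect detectable at 80% power, (z + 0.84) × √(2/48), then rises from 0.57 SD to 0.71 SD (6 tests) or 0.77 SD (15 tests). Control within families does not control the whole trial: with no true effects, the chance of at least one false claim across the primary and four families is about 1 − 0.95⁵ = 23% if independent, and about 10% at correlation 0.7. The report should say so.

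### Does adding 10 per group to cover a 20% loss leave the trial short of the number it needs?

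*Combined protocol and SAP*

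**What the plan says.** Under 4. Methods, Sample size calculations, the plan uses the usual normal-approximation formula for comparing two means. The outcome is glucose. The inputs, taken from an earlier supplementation trial by the same group, are a standard deviation of 68.9 mg/dL, a difference of 40 mg/dL, and normal deviates of 1.96 and 0.84 (two-sided 5% and 80% power, neither stated in words). The printed result is 46, rounded at once to 50 per group.

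The loss allowance comes next: "Accounting for a 20% loss at follow-up, we added 10 subjects, resulting in 60 subjects per group". The Study design paragraph agrees with that total. It plans 120 adults, "divided in two groups: supplement and placebo (60 per group").

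The plan does not show how the 10 was obtained, and it does not say how many per group it expects to remain at 24 weeks. Data Collection and Statistical Analysis names no specific test for the group comparison. It leaves the choice between parametric and non-parametric methods to a normality check.

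**The concern.** Ten is 20% of 50, so the allowance appears to have been worked out on the number wanted at the end and not on the number enrolled. To keep n patients after a loss fraction L, one enrols n/(1 − L). The plan's figure matches n × (1 + L), which is always too small. Someone who reads the paragraph as protecting 50 per group would believe that 100 patients remain after a 20% loss, when 96 do.

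There is a second oddity. The formula gives 46.52, and a sample size is rounded up, so the printed 46 should be 47.

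If either slip had carried through to a sample below the calculated requirement, the trial would have been planned with less than its intended 80% power for glucose, the only outcome for which a calculation is given.

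**Working it through.** **Inputs** (all from Sample size calculations): s = 68.9 mg/dL, so s² = 4747.21; d = 40 mg/dL; deviates 1.96 and 0.84; loss 20%; 10 added per group; 60 enrolled per group.

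**1. The plan's base figure.**
N = 2 × 4747.21 × (1.96 + 0.84)² / 40² = 2 × 4747.21 × 7.84 / 1600 = 46.52.
The plan prints 46; rounding up gives 47. It then moves to 50, so the choice between 46 and 47 feeds no later figure.

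**2. The plan's enrolled figure.**
50 × (1 + 0.20) = 60, which matches the plan. By contrast, 50 / (1 − 0.20) = 62.5, or 63 per group, does not match. That the 10 was computed as 20% of 50 is inferred from this match.

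**3. What remains of 60.**
60 × 0.20 = 12 lost, leaving 48 per group (96 in total, against 100).
Largest loss that keeps 50: 10/60 = 16.7%.

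**4. Comparison with the calculated requirement.**
46.52/0.8 = 58.2 and 47/0.8 = 58.75, so 59 enrolled per group would be enough. The plan has 60. The 48 who remain exceed the required 47.

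**5. Power for 40 mg/dL with SD 68.9, two-sided 5%.**
Normal approximation: Φ(d / (s√(2/n)) − 1.96). At n = 48, s√(2/n) = 14.06, the ratio is 2.844, and Φ(0.884) = 81.2%. The t-test column uses the noncentral t distribution with 2n − 2 degrees of freedom.

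| n per group | Normal approximation | t-test |
|---|---|---|
| 46 | 79.5% | 78.7% |
| 47 | 80.4% | 79.5% |
| 48 | 81.2% | 80.4% |
| 50 | 82.7% | 82.0% |
| 60 | 88.9% | 88.4% |

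The t-test requirement for 80% power solves to 47.55, so 48 per group, and 48/0.8 = 60 exactly.

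**6. Size of the shortfall.**
Going from 50 to 48 costs 82.7 − 81.2 = 1.5 points by the normal approximation and 82.0 − 80.4 = 1.6 points by the t-test. The difference detectable with 80% power (t-test) moves from 39.0 to 39.8 mg/dL, still below the planned 40.

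**The case for a change.** The strongest case for acting is that the paragraph is the sole justification for enrolling 120 people and that its loss allowance can be faulted with one multiplication. The allowance is stacked on 50, which suggests that 50 was the number to be protected. The margin is also thin. For a t-test, 48 is exactly the minimum, and one more loss per group (13 of 60, or 21.7%) takes power to 79.5%. A reader who thinks 50 remain would see slack at 20% loss where a t-test has almost none.

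The arithmetic in this stands, and so does the remark about the margin. What does not stand is the step from there to a defect in the design. The plan never states that 50 will remain; that is the reader's inference. The 50 came from rounding up 46.5, and that rounding absorbs what the allowance lacks. By the plan's own formula, 47 per group still gives 80.4%, so 13 losses in each group would be tolerable.

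A further point concerns the test. If the non-parametric route were taken and the data were in fact normal, a rank test has an asymptotic efficiency of 3/π, about 0.955 (a mathematical result, not a figure in the documents). Then 48 patients act like 48 × 0.955 = 45.8, with t-test power of about 78.5%, and 50 act like 47.75, with about 80.2%. This is a reason not to call the target met under every possible analysis. It does not justify a different sample size: the plan would use the non-parametric route when normality is doubtful, and with skewed data a rank test may do better than the t-test.

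**Conclusion.** The observation is correct, but no change to the plan follows. Sixty per group leaves 48 after a 20% loss, not 50. Those 48 exceed the calculated requirement of 46.5 (47 rounded up) and give 81.2% power by the plan's normal approximation, or 80.4% by a two-sided 5% t-test. The cost is about 1.5 points of power, or 0.8 mg/dL in detectable difference. The 46 in place of 47 is a rounding slip with no consequence.

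A correction would leave the enrolled number, the tests, the endpoints and the power target where they are, so there is nothing to gain from it. Anyone reporting the trial can simply say that 48 per group were expected after a 20% loss.

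This rests on the plan's stated SD of 68.9 mg/dL and difference of 40 mg/dL, whose source could not be checked here, on a loss of no more than 20% in each group, and on a comparison of means by t-test or normal approximation. It concerns glucose only and does not support the plan's separate claim that this sample size is enough for all other indicators.
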